6.7.3. Infusion-Related Reactions

| Dinutuximab Treatment Modification | |
|---|--|
| Infusion Reactions Severity (NCI CTCAE v4.03)* | |
| Grade 1 | Mild transient reaction; infusion interruption not indicated; intervention not indicated (e.g., transient flushing or rash, drug fever <38°C) |
| Grade 2 | Therapy or infusion interruption indicated but responds promptly to symptomatic treatment (e.g., antihistamines, NSAIDs, opioid analgesics, IV fluids); prophylactic medications indicated for ≤24 hrs (e.g., rash, flushing, urticaria, dyspnea, drug fever ≥38°C) |
| Grade 3 | Prolonged (e.g., not rapidly responsive to symptomatic medication and/or brief interruption of infusion); recurrence of symptoms following initial improvement; hospitalization indicated for clinical sequelae (e.g., symptomatic bronchospasm, requiring parenteral medication(s), with or without urticaria; allergy-related edema/angioedema, hypotension) |
| Grade 4 | Life-threatening consequences; urgent intervention indicated |

| | |
|---------|---|
| Grade 1 | Decrease dinutuximab infusion rate by 50% and monitor closely for any worsening. |
| Grade 2 | 
Interrupt dinutuximab infusion, administer appropriate therapy (e.g., antihistamines, NSAIDs, IV fluids, steroids, and then restart the dinutuximab infusion with a decrease in the infusion rate of 50% and monitor closely for any worsening.
 
Premedicate in all future cycles with:
 
 • Dexamethasone 20 mg PO administered approximately 12 and 6 hours before dinutuximab, • Diphenhydramine (or its equivalent) 50 mg IV 30 to 60 minutes prior to dinutuximab, and • Cimetidine 300 mg or ranitidine 50 mg IV 30 to 60 minutes before dinutuximab infusion. • If re-starting dinutuximab infusion results in grade 2 or higher toxicity, stop infusion (and record infused dose). 
Reduce dose of dinutuximab by 1 dose level in next cycle.
 |
| Grade 3 | 
Immediately stop the dinutuximab infusion and disconnect infusion tubing from the subject.
 
Administer epinephrine, bronchodilators, antihistamines, glucocorticoids, IV fluids, vasopressor agents, oxygen, etc., as medically indicated.
 
Permanently discontinue dinutuximab. (If standard practice and risk-benefit in the judgment of the Investigator warrants continued treatment, administering dinutuximab in future cycles can be considered only if additional precautions (re. premedications and infusion rate) are followed and after consultation with and approval of the Medical Monitor.)
 |
| Grade 4 | Immediately stop the dinutuximab infusion and disconnect infusion tubing from the subject. |

| | |
|--|--|
| 
(e.g., event characterized by rapid onset, often within minutes, of airway obstruction [bronchospasm, stridor, hoarseness], urticaria, and/or hypotension
 | 
Administer epinephrine, bronchodilators, antihistamines, glucocorticoids, IV fluids, vasopressor agents, oxygen, etc., as medically indicated. Permanently discontinue dinutuximab.
 |
|--|--|

*Grades are per NCI CTCAE v4.03. Examples of signs and symptoms are provided in addition to aid diagnosis.

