Subjects randomized to Group A or Group B will receive irinotecan at a dose of 350 mg/m² on Day 1 of each cycle.

Subjects randomized to Group B will also receive dinutuximab on Day 1 of each cycle beginning with a starting dose of 16 mg/m² IV. Dose escalation and de-escalation for dinutuximab will occur as in Part 1. The maximum dose of dinutuximab that may be administered is 17.5 mg/m² (If this dose is reached, the last dose increment would be 1.5 mg/m². If the dose is reduced from 17.5 mg/m², the initial dose decrement would be 1.5 mg/m² to 16 mg/m²).

Subjects randomized to Group C will receive topotecan 1.5 mg/m² IV for 5 consecutive days of each cycle.

One cycle is 21 days in duration.

There is a 2-day window around administration of study drugs on Day 1 of each cycle except for the first cycle (initial treatment should begin within 3 working days of enrollment or randomization). All subjects (Part 1 and Part 2) will be treated during the study until Response Evaluation Criteria in Solid Tumors (RECIST)-determined disease progression or intolerance. All subjects will be followed for disease progression even those discontinuing study drug for other reasons (e.g., intolerance).

An end of treatment (EOT) visit will occur within approximately 30 days after the time the Investigator decides to discontinue all study drugs (dinutuximab and/or chemotherapy) or prior to the initiation of subsequent treatment, whichever occurs first.

Immunogenicity follow-up will continue for subjects receiving dinutuximab for up to 16 weeks following the last dose of dinutuximab to assess anti-drug antibodies (ADA) and neutralizing antibodies (NAb).

[figure not shown]
Monthly follow-up for survival will begin after the EOT visit and will continue until the subject has withdrawn consent, is lost to follow-up, has died, or until the Sponsor makes a decision to close the study. It is important that all subjects are followed for survival.

No crossover between groups is allowed given OS is the primary endpoint.

See [Figure 1](#) for study schema.

Figure 1. Study Schema

Part 1

Part 2

One cycle = every 21 days (q21d).

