6.7.1. Dose Reduction Levels for Dinutuximab

| Dinutuximab Dose Levels | | | |
|----------------------------------|-----|----|----|
| | 0 | -1 | -2 |
| Dinutuximab (mg/m ²) | 16* | 14 | 12 |

*Part 2 starting dose
Subsequent doses may be adjusted in 2 mg/m² decrements per cycle depending upon individual subject tolerance to as low as 8 mg/m²/day (Part 1 and Part 2).

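### Section 6.7.3 does not say which row governs return of the same symptoms on restart after a Grade 2 infusion reaction, so the Grade 2 row can be read as allowing re-dosing without the Grade 3 approval step

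*Protocol*

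**What the plan says.** All of the conflicting text is in Protocol section 6.7.3.

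- **Grade 2 definition.** The reaction needs treatment or an interruption but responds promptly.
- **Grade 2 action.** Interrupt, treat, then "restart the dinutuximab infusion with a decrease in the infusion rate of 50" percent. Premedicate in all future cycles. Within the premedication list stands the restart rule: "If re-starting dinutuximab infusion results in grade 2 or higher toxicity, stop infusion (and record infused dose". The row closes with "Reduce dose of dinutuximab by 1 dose level in next cycle". It does not mention re-grading, the Grade 3 row or the Medical Monitor.
- **Grade 3 definition.** One of several elements separated by semicolons is "recurrence of symptoms following initial improvement". No severity threshold is attached to it.
- **Grade 3 action.** Stop at once and discontinue dinutuximab permanently. Later dosing may be considered "only if additional precautions (re. premedications and infusion rate) are followed and after consultation with and approval of the Medical Monitor".
- **Footnote.** "Grades are per NCI CTCAE v4.03". It makes no exception for events on restart.

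Section 6.7.1 sets the dose levels at 16, 14 and 12 mg/m², with further "decrements per cycle depending upon individual subject tolerance to as low as" 8 mg/m². From 17.5 mg/m², section 5.1 says "the initial dose decrement would be 1.5" mg/m².

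**The concern.** The Grade 2 row itself creates the sequence in which a recurrence can happen: the symptoms improve, then the subject is re-exposed. The row then gives a rule for toxicity on restart, and the words covering Grade 2 and above bring Grade 3 events within that rule. A site reading down the row finds the stop instruction and then a reduced dose for the next cycle. A site that re-grades the event finds permanent discontinuation, or approval before any rechallenge.

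What can be lost is the default of stopping dinutuximab and the Medical Monitor's decision before a subject who has reacted twice in one infusion is exposed again. Section 5.2 plans approximately 200 centers, so the answer should not depend on each site inferring the re-grade.

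**Working it through.** The plan gives no figure to reproduce here. The check sets the two rows side by side for one event: a Grade 2 reaction improves, the infusion is restarted, and the same symptoms return at Grade 2 intensity.

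1. **Which grade is it?** If each element of the Grade 3 definition suffices alone, the event is Grade 3, because recurrence after improvement is listed as its own element.

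2. **Which action applies?**

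| | Grade 2 row | Grade 3 row |
|---|---|---|
| Current infusion | Stopped | Stopped |
| Later cycles | Given with premedication, one level lower | None by default; rechallenge by exception |
| Medical Monitor | No step | Consultation and approval before rechallenge |
| Next planned dose, if given | 16 − 2 = 14 mg/m², or 17.5 − 1.5 = 16 mg/m² | No dose reduction stated |

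The rows agree on the current infusion. They differ on later cycles and on approval.

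3. **Is the overlap only a gap in detail?** If recurrence is always Grade 3, the Grade 2 part of the restart rule's trigger is left with little beyond new and different symptoms. Such symptoms are not a recurrence and raise no conflict. That the rule names Grade 2 at all makes it plausible that it was meant to cover the original symptoms coming back, which is what the Grade 3 definition claims.

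4. **Does another section settle it?** Section 6.1 refers back to 6.7.3 for premedication. Section 6.2 deals with pain during the infusion. Section 6.6 asks for Medical Monitor discussion only for delays beyond 7 days. Elsewhere the protocol does write recurrence rules: section 6.7.2 for Grade 3 pain after a dose reduction, and section 6.7.8 for neurologic eye disorders. Section 6.7.3 has no equivalent, and the SAP does not address the matter.

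5. **How often?** Neither document gives a rate for recurrence on restart.
   - At the first Part 1 cutoff (section 1.15), 12 subjects had received 12 + 12 + 9 + 4 + 1 = 38 cycles, and no dinutuximab dose reduction had been required. The Grade 2 row mandates a reduction in the next cycle, so this suggests that few such reactions occurred.
   - The evidence is thin. Only 38 − 12 = 26 cycles were second or later cycles, where a reduction could show. Three subjects had data at 16 mg/m², the Part 2 starting dose.
   - The later safety review, with 8 of 12 subjects at 16 mg/m² or higher, reported comparable tolerability but no count of infusion reactions.

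**The case against.** The strongest answer is that the rows can be applied together. Actions are indexed by grade. The restart rule orders only two things, stopping and recording the dose, and both concern the current infusion. The one-level reduction is a separate statement that reads as applying to Grade 2 reactions in general, and its link to a failed restart rests on position alone. On that view, an event that meets Grade 3 is stopped under either row and then follows the Grade 3 row. This reading is available and is arguably the safer one. What stands against it is that the protocol does not state it, and that the text most specific to restart sits in the Grade 2 row.

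There is also real mitigation. The Grade 2 row requires a corticosteroid, an antihistamine and an H2 blocker in later cycles. Section 6.1 requires close monitoring at every infusion. Section 12.8 has the DMC review severe allergic reactions. Section 9.4 requires SAEs to be reported within 24 hours, so a serious recurrence would normally reach the sponsor before the next 21-day cycle; a non-serious one need not. None of these replaces an individual decision before re-exposure.

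A reader might draw stronger conclusions that the documents do not support:

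- *That the protocol orders re-dosing after a Grade 3 reaction.* It does not; the text is ambiguous.
- *That a Grade 4 reaction on restart could be re-dosed.* The Grade 4 row is unconditional, and nothing suggests a site would override it.
- *That the two readings differ by nearly a full dose against none.* The Grade 3 exception permits rechallenge and states no dose cut. In addition, 16 and 17.5 mg/m² are planned doses, and the infusion in question was stopped partway.
- *That the 25% versus 1% Grade 3 or 4 infusion-reaction rates in section 1.8 size the problem.* They come from children who also received cytokines, and they do not count recurrences on restart.

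**Conclusion.** The point holds as an unresolved ambiguity between two safety rules in one table. It rests on one assumption: that each semicolon-separated element of the Grade 3 definition is sufficient alone. That is the natural reading, but the table does not state it. If recurrence counted as Grade 3 only at some higher intensity, the conflict would narrow to recurrences of that intensity.

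The reach is limited to dinutuximab dosing in later cycles and to the approval step. The number of subjects affected is unknown and probably low. The primary OS comparison by ITT, its alpha and its power are unaffected. The point merits correction because it concerns re-exposure after a repeated reaction and costs little to settle.

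**What to change.** Move the restart rule out of the premedication bullets and add a sentence to the Grade 2 row along these lines: *If toxicity on restart meets the Grade 3 definition (including recurrence of the original symptoms after improvement) or is Grade 4, follow the Grade 3 or Grade 4 row for all later dosing, including Medical Monitor approval before any rechallenge after Grade 3; the premedication and one-level reduction in this row apply only to reactions that remain Grade 2.*

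This can go into the next amendment, with a memo to sites in the meantime. The analysis does not change. The downside is that the recurrence element carries no severity threshold, so some subjects with a low-intensity recurrence would need Medical Monitor approval or would stop dinutuximab. If the sponsor finds that too strict, it could instead state expressly that a recurrence of Grade 2 intensity stays in the Grade 2 row. Either statement removes the ambiguity; the first keeps the table's own default of stopping unless approval is given.

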6.7.4. Neuropathy

Peripheral sensory neuropathy

Peripheral sensory neuropathy is a disorder characterized by inflammation or degeneration of the peripheral sensory nerves.

| Peripheral Neuropathy | | Dinutuximab Treatment Modification |
|------------------------------|--|--|
| Severity (NCI CTCAE v4.03) | | |
| Grade 1 | Asymptomatic; loss of deep tendon reflexes or paresthesia | 
Decrease dinutuximab infusion rate by 25% and monitor closely for any worsening.
 
Administer non-opiate pain medication, as needed. Morphine and medications to treat neuropathic pain may also be considered (see below).
 |
| Grade 2 | Moderate symptoms; limiting instrumental ADL | 
Decrease dinutuximab infusion rate by 50% and monitor closely for any worsening.
 
Administer opioid analgesics (morphine sulfate or morphine equivalent such as hydrocodone, hydromorphone, oxycodone). Consider use of medications used to treat neuropathic pain (e.g., gabapentin, pregabalin, duloxetine, venlafaxine).
 
Once symptoms resolve to <Grade 2, gradually increase dinutuximab infusion rate as tolerated.
 
Reduce dose of dinutuximab by 1 dose level in next cycle. Once maximal symptoms per cycle have resolved <Grade 2, the dose of dinutuximab should be increased in subsequent cycle(s) per Table 5.
 |
| Grade 3 | Severe symptoms; limiting self care ADL | 
Hold dinutuximab until resolution.
 
Administer opioid analgesics per above. Morphine drip may also be considered.
 
Reduce dose of dinutuximab by 2 dose levels in next cycle. Once maximal symptoms per cycle have resolved <Grade 2, the dose of dinutuximab should be increased in subsequent cycle(s) per Table 5.
 
Permanently discontinue dinutuximab in subjects with Grade 3 sensory neuropathy that interferes with daily activities for more than 2 weeks.
 |
| Grade 4 | Life-threatening consequences; urgent intervention indicated | 
Permanently discontinue dinutuximab immediately upon awareness.
 |

Peripheral motor neuropathy

Peripheral motor neuropathy is a disorder characterized by inflammation or degeneration of the peripheral motor nerves.

| Motor Neuropathy | | Dinutuximab Treatment Modification |
|----------------------------|--|--|
| Severity (NCI CTCAE v4.03) | | |
| Grade 1 | Asymptomatic; clinical or diagnostic observations only; intervention not indicated | Hold dinutuximab until resolution (Grade 0). Notify Medical Monitor immediately. Permanently discontinue dinutuximab in subjects with Grade 1 motor neuropathy that does not resolve within 2 weeks. |
| Grade 2 | Moderate symptoms; limiting instrumental ADL | Permanently discontinue dinutuximab immediately upon awareness. |
| Grade 3 | Severe symptoms; limiting self care ADL; assistive device indicated | Permanently discontinue dinutuximab immediately upon awareness. |
| Grade 4 | Life-threatening consequences; urgent intervention indicated | Permanently discontinue dinutuximab immediately upon awareness. |

Transverse Myelitis

Transverse myelitis is a disorder characterized by inflammation involving the spinal cord. Symptoms include weakness, paresthesia, sensory loss, marked discomfort and incontinence.

Discontinue dinutuximab immediately if transverse myelitis is suspected and contact the Medical Monitor.

Reversible Posterior Leukoencephalopathy Syndrome (RPLS)

Reversible Posterior Leukoencephalopathy Syndrome (also known as Posterior Reversible Encephalopathy Syndrome, RPLS or PRES) is a disorder characterized by severe headache, hypertension, visual changes, lethargy and/or seizure.

| RPLS | | Dinutuximab Treatment Modification |
|----------------------------|--|---|
| Severity (NCI CTCAE v4.03) | | |
| Grade 1 | Asymptomatic; clinical or diagnostic observations only; intervention not indicated | Hold dinutuximab until resolution (Grade 0). Notify the Medical Monitor immediately. |
| Grade 2 | Moderate symptoms; limiting instrumental ADL | Permanently discontinue dinutuximab immediately upon awareness. Immediately notify the Medical Monitor. |
| Grade 3 | Severe symptoms; very abnormal imaging studies; limiting self-care ADL | Permanently discontinue dinutuximab immediately upon awareness. Immediately notify the Medical Monitor. |
| Grade 4 | Life-threatening consequences; urgent intervention indicated | Permanently discontinue dinutuximab immediately upon awareness. Immediately notify the Medical Monitor. |

6.7.5. Clinical Tumor Lysis Syndrome (TLS)

Clinical TLS is present when laboratory TLS is accompanied by an increased creatinine level and a constellation of clinical signs and symptoms including any symptoms of hypocalcemia, such as anorexia, vomiting, cramps, seizures, spasms, altered mental status, and muscle tetany and symptoms of hyperkalemia, such as weakness and paralysis.

| Clinical TLS | Dinutuximab Treatment Modification |
|---------------------|--|
| Onset of reaction | Hold dinutuximab until resolution (Grade 0). Institute cardiac rhythm monitoring, fluids as clinically indicated, and serial laboratory monitoring per institutional standard. Correct electrolyte abnormalities, monitor renal function and fluid balance. Administer therapeutic (rasburicase or other approved uric acid-lowering agent) and supportive care, including dialysis, as clinically indicated. Note: There is a potential for immunogenic interaction between rasburicase and dinutuximab. |
| After resolution | In next cycle, resume dinutuximab treatment at an infusion rate that is 50% of the previous rate. Gradually increase the infusion rate as tolerated. |

6.7.6. Hypotension Requiring Medical Intervention

Hypotension requiring medical attention refers to symptomatic hypotension.

| Symptomatic Hypotension | Dinutuximab Treatment Modification |
|--------------------------------|--|
| Onset of reaction | Interrupt dinutuximab infusion. Institute clinic standard treatment. |
| After resolution | Resume dinutuximab infusion at 50% of the previous rate. If blood pressure remains stable, gradually increase the infusion rate as tolerated. |

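### Protocol Section 6.7.6 allows a half-rate restart after any symptomatic hypotension and does not exclude the Grade 3 and 4 infusion reactions for which Section 6.7.3 rules out a restart

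*Protocol*

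**What the plan says.** Section 6.7.6 defines its subject in one line: "Hypotension requiring medical attention refers to symptomatic hypotension". At onset the infusion is interrupted and the clinic's standard treatment given. After resolution the instruction is "Resume dinutuximab infusion at 50% of the previous rate. If blood pressure remains stable, gradually increase the infusion rate as tolerated". The section contains nothing else: no CTCAE grade, no row for a second episode and no reference to another section.

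Section 6.7.3 grades infusion-related reactions and lists hypotension among the example signs at Grade 3 and again at Grade 4. For both grades the site must stop the infusion at once, disconnect the tubing, give emergency treatment as needed (vasopressors and IV fluids are on the list) and permanently discontinue dinutuximab. Grade 4 has no exception. Grade 3 has one: if the investigator judges that risk and benefit warrant it, future cycles can be considered with additional precautions and Medical Monitor approval. The Grade 3 definition also covers symptoms that come back after first improving. A footnote says the example signs are there to help diagnosis.

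**The concern.** A subject who becomes symptomatically hypotensive during a dinutuximab infusion falls within 6.7.6 by its own definition. If the event is also a Grade 3 or 4 infusion reaction, the subject falls within 6.7.3 as well. One section then says to resume after recovery, the other says not to, and no text settles which applies.

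At stake is re-exposure to the antibody within the same infusion after a severe or life-threatening reaction. Handling could also differ between sites: Section 5.2 expects about 200 centers, and 184 subjects are planned for Group B. The primary overall survival comparison uses all randomized subjects as assigned, so the ambiguity does not touch its validity.

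**Working it through.** The plan gives no figure to reproduce and the point needs no arithmetic. The check sets the two sections side by side.

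| Element | Section 6.7.6 | Section 6.7.3, Grade 3 | Section 6.7.3, Grade 4 |
|---|---|---|---|
| Hypotension covered? | Yes, all symptomatic cases | Yes, as an example sign | Yes, as an example sign |
| At onset | Interrupt and treat | Stop, disconnect, treat | Stop, disconnect, treat |
| Same infusion | Resume at half rate after resolution | No restart provided for | No restart provided for |
| Future cycles | Not addressed | Permanent discontinuation unless the Medical Monitor approves, with precautions | Permanent discontinuation |
| Recurrence | Not addressed | Return of symptoms after improvement is itself a Grade 3 criterion | Not addressed separately |
| Pointer to the other section | None | None | None |

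Four steps follow.

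1. *Do both sections address the same moment?* Yes. Section 6.7.6 begins by interrupting the infusion, so it covers events during infusion, as 6.7.3 does.

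2. *Does resuming in 6.7.6 mean the same infusion?* The text supports that. Section 6.7.5 (tumor lysis syndrome) says explicitly that treatment resumes in the next cycle. Section 6.7.6 has no such words and ties the later rate increase to blood pressure staying stable.

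3. *Does the Grade 3 exception remove the conflict?* No. It concerns future cycles only. It makes permanent discontinuation the default at Grade 3 rather than absolute, but it never permits a restart of the interrupted infusion.

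4. *What happens if hypotension returns after a 6.7.6 restart?* Section 6.7.6 conditions only the rate increase on stable pressure and does not say to stop. Under 6.7.3, symptoms returning after improvement meet a Grade 3 criterion. Even its Grade 2 row stops the infusion when a restart brings back toxicity of grade 2 or higher.

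Both missing devices appear elsewhere in 6.7. Section 6.7.2 points to 6.7.4 for neuropathy, and 6.7.8 has a row for first recurrence.

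Severe hypotension is foreseeable from the protocol's own background. Section 1.8 reports Grade 3 or 4 hypotension in 16% versus 0% in the pediatric Phase 3 trial. Table 3 reports Grade 3 hypotension in 2 of 16 patients (13%) given dinutuximab with irinotecan and temozolomide. Those were children who also received GM-CSF (and IL-2 in the Phase 3 trial), with dinutuximab on four days per cycle. The rates cannot be carried over to adults dosed once per cycle without cytokines.

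**The case against.** The strongest reply is that the two sections have different subjects: 6.7.3 covers hypersensitivity and infusion reactions, and 6.7.6 covers isolated hypotension. There is support for this. Section 6.1 sends sites to 6.7.3 for premedication after an earlier hypersensitivity reaction. The other Grade 3 and 4 examples, such as bronchospasm, angioedema and airway obstruction, look allergic. Section 1.8 lists infusion reactions and hypotension as separate reactions. Once an event is graded as a Grade 3 or 4 infusion reaction, 6.7.3 applies on its own terms, and 6.7.6 does not claim to override it.

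Much of this stands. It is the reading most clinicians would probably choose, and it is why the point is minor. But it has to be inferred. The pointer in 6.1 concerns premedication, the background rates are not instructions, and 6.7.6 defines its scope as symptomatic hypotension without qualification. Close monitoring (6.1) and the general provision in 6.5 for stopping treatment that harms the patient reduce the risk without saying which section governs.

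A reader might also infer a conflict at Grade 2, because its criterion, "Therapy or infusion interruption indicated but responds promptly to symptomatic treatment", resembles what 6.7.6 orders in every case. The documents do not carry that far. Hypotension is not among the Grade 2 examples ("rash, flushing, urticaria, dyspnea, drug fever"), and both sections restart at half rate. The Grade 2 line "Reduce dose of dinutuximab by 1 dose level in next cycle" comes straight after the failed-restart bullet, so it may apply only after a failed restart. Table 5 and Section 6.7.1 also allow a 2 mg/m² reduction for toxicity in general, so a contrast of 14 mg/m² under one section with 16 or 17.5 mg/m² under the other is not established.

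Sending all Grade 2 hypotension to 6.7.3 would nearly empty 6.7.6. Brief, fluid-responsive episodes would then bring dexamethasone (two 20 mg doses, 40 mg in all) in every later cycle, in a protocol that discourages corticosteroids as anti-emetics. That is a debatable trade-off, not a correction.

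**Conclusion.** The point holds for Grade 3 and 4 infusion reactions and for recurrence after restart. For those events 6.7.6, read literally, allows a same-infusion restart that 6.7.3 does not, and no text resolves it. Severity is minor: the effect is on patient safety and consistent dosing, and the sensible reading avoids the problem.

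The size cannot be put as a number of subjects. A reader might apply the 16% pediatric rate to the 184 Group B subjects, but that rate counts severe hypotension overall, not hypotension that is also a Grade 3 or 4 infusion reaction, and it comes from a different population and regimen. The only data on this regimen are from Part 1 (Section 1.15): 12 adults, with no hypotension among the nine listed serious adverse events and no dinutuximab dose reductions at that cutoff. That sample is too small to give a rate.

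The conclusion rests on taking 6.7.6 at its words and on its resumption referring to the interrupted infusion, as the contrast with 6.7.5 indicates.

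**What to change.** Add to Section 6.7.6: *This section applies to symptomatic hypotension that is not part of a Grade 3 or 4 infusion reaction. If hypotension meets Grade 3 or 4 infusion-reaction criteria, do not resume and follow Section 6.7.3. If symptomatic hypotension recurs after restart, stop the infusion for that cycle and manage per Section 6.7.3.* Put a matching pointer in the Grade 3 and Grade 4 rows of 6.7.3. Leave the Grade 2 row unchanged.

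The cost is a few sentences and two pointers at the next amendment, with a memo to sites. No new data, visits or subjects are needed, and the statistical analysis is unaffected.
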